2.2 Safety

Safety of the test and reference products will be compared by evaluating the nature, severity and frequency of their adverse event profiles. All adverse events that occur during the study (from the moment a subject signs an informed consent/assent) will be recorded. Descriptions of reactions or complaints will include the approximate date of onset, the date the adverse event ended, the severity of the adverse event, and the outcome. Comparisons between the treatment groups will be made by tabulating the frequency of subjects with one or more adverse events (classified into MedDRA terms) during the study. Pearson's Chi-Square test or Fisher's Exact test, whichever is most appropriate, will be used to compare the proportion of subjects in the two active treatment groups with any adverse event. [REDACTED]

Protocol No: PRG-NY-15-002

of the subject's adverse events (AEs). At this visit, the Follow-Up Telephone Call/Day15, Visit 3/Day 29 and Visit 4/Day 57 will be scheduled.

A Follow-Up Telephone Call will be made by study staff to the subject at Day 15 to review and assess subject compliance (diary completion), record AEs, update concomitant medication use, and to remind the subjects of the protocol requirements and next study visit schedule.

At Visit 3/Day 29 (Interim) and Visit 4/Day 57 (End of Study), subjects will be asked if they experienced any adverse events, taken any concomitant medications and generally complied with protocol requirements. The diary dispensed at Visit 2 will be collected and reviewed with the subject, and a new diary will be dispensed at Visit 3/Day 29. The diary dispensed at Visit 3 will be collected and reviewed at Visit 4/Day 57. Safety will be assessed by the monitoring of all adverse events (AEs) and clinically significant changes from Visit 1/Day 1 (Baseline) and an application site reaction assessment will be conducted at Visit 3/Day 29 and Visit 4/Day 57.

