7. ADVERSE REACTIONS

The potential adverse reactions of generic Ingenol Mebubate Topical Gel 0.05% are anticipated to be similar to those observed in Picato[®] Topical Gel (Ingenol Mebutate Topical Gel 0.05%). The most common adverse reactions related to treatment with Picato[®] Topical Gel include local skin reactions, application site pain, application site pruritus, application site irritation, and nasopharyngitis. Eye disorders, including severe eye pain, eyelid edema, eyelid ptosis, and periorbital edema can occur after exposure. Severe local skin reactions such as vesiculation/pustulation, erosion/ulceration can occur.

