8.1.5 Safety and Adverse Events Analysis

The frequency and percent of subjects with adverse events will be summarized by MedDRA (Version 15.1) system organ class and preferred term and by severity and relationship to study drug for all three treatment groups. The adverse events reported by at least five percent of the subjects in any treatment group will also be tabulated. The comparable safety of the Test and Reference treatments will be evaluated by statistical comparison of the proportion of subjects who reported any adverse events. The test and reference treatments' frequency and distribution of application site reactions of erythema, flaking/scaling, crusting, swelling, vesiculation/postulation, and erosion/ulceration will be summarized and compared descriptively. Safety comparisons will be performed only for the safety intent-to-treat population.

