5.1 Methodological Considerations

The study will be conducted under the same protocol across all the sites. No formal statistical analyses are planned to evaluate the consistency of efficacy results across the multiple clinical sites. These results, however, will be tabulated and if a site's efficacy data are obviously inconsistent with the results across all sites, this will be explored and addressed in the final study report.

Two-sided hypothesis testing will be conducted for all the tests. Resulting p-values less than 0.05 will be considered statistically significant unless noted otherwise. No adjustments of p-values for multiple comparisons will be made. No interim analyses are planned. SAS software will be used for all data analyses and tabulations.

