5.6 Safety Variables and Analyses

Duration of Treatment and Medication Compliance

Number of applications, days of exposure, and compliance rate will be summarized by treatment group using descriptive statistics. For each subject, the overall duration of treatment (days) will be calculated using the following formula:

$$\text{(Date of last application of study medication)} - \text{(Date of first application of study medication)} + 1.$$

Medication compliance rate (%) will be calculated for each subject as follows:

$$\text{(Total number of applications used)} / \text{(Expected number of applications)} * 100\%.$$

Subjects who complete the study are expected to have 2 applications. [REDACTED]

[REDACTED] For prematurely discontinued subjects, expected number of applications will be determined based on the

overall duration of treatment by the time of discontinuation. Descriptive summaries of exposure and medication compliance rate will be provided by treatment group for the ITT subjects

Adverse Events

Adverse events (AEs) will be coded in MedDRA, version 15.1. Treatment-Emergent Adverse Event (TEAE) is defined as any AE occurs on or after applying the first dose of study drug. Number and percent of subjects reporting TEAEs will be tabulated by treatment group. Summaries will be presented by body system and preferred term for the ITT population, and further by severity and relationship to study medication. TEAEs reported by 5% or more subjects for any treatment group will also be summarized. In the summaries of incidence rates (frequencies and percentages), severity and relationship to study drug, subjects who report more than one event that are mapped to the same preferred term will be counted only once under the strongest severity and relationship, accordingly Fisher's exact test will be used to compare the proportions of subjects of the two active treatment groups who report any TEAE.

Treatment-Emergent Serious Adverse Events (TESAEs) will be discussed within the clinical study report. TESAEs and TEAEs that led to treatment interruption or discontinuation will be presented in data listings.

Concomitant Medications

Concomitant medications will be coded using the WHO Drug Dictionary, version September 2014, and will be presented in data listings.

Application Site Reactions

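### The only visible Test-Reference safety test is on any TEAE, which pools application site events with unrelated ones and so loses sensitivity to a local difference between the products

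*SAP*

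**What the plan says.** SAP 5.6 (Adverse Events) states that Fisher's "exact test will be used to compare the proportions of subjects of the two active treatment groups who report any TEAE". Its definition of a TEAE covers every adverse event from the first dose onward, whatever its body site or relationship to treatment. SAP 5.1 sets the rules: "Two-sided hypothesis testing will be conducted for all the tests", and "Resulting p-values less than 0.05 will be considered statistically significant unless noted otherwise". It makes no multiplicity adjustment.

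Protocol 8.1.5 says what the comparison is for: "The comparable safety of the Test and Reference treatments will be evaluated by statistical comparison of the proportion of subjects who reported any adverse events".

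Protocol 5.10 decides which local events reach the adverse event data. The six graded reactions (erythema, flaking/scaling, crusting, swelling, vesiculation/pustulation, erosion/ulceration) count as adverse events only if they lead to interruption of medication, withdrawal from the study or a new concomitant medication. Other local reactions, such as pain, pruritus and infection, are always adverse events. Protocol 7 lists the common reactions as "local skin reactions, application site pain, application site pruritus, application site irritation, and nasopharyngitis", so four of the five are local.

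The rest of the visible safety plan is descriptive. SAP 5.6 tabulates TEAEs by body system and preferred term, and by severity and relationship. It adds a table of TEAEs at 5% or more in any group, and tabulates the graded reactions by treatment group and visit.

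No adverse event rate, safety margin, safety confidence interval or power for the safety test is visible. The sample size (Protocol 8.1.3) and allocation ratio (Protocol 6.2.4) are redacted.

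**The concern.** Test and Reference are both ingenol mebutate gel 0.05%. If the generic formulation is less well tolerated, the difference should appear mainly at the application site. The tested variable is not built to show that. It leaves out the graded reactions that meet no trigger, and it mixes the remaining local events with events that have nothing to do with the formulation.

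The direction of the error matters. In a superiority test, low sensitivity works against the sponsor. Here the p-value feeds a statement of comparable safety, so low sensitivity works in favour of that statement. For efficacy, SAP 5.5 guards against reading non-significance as similarity by requiring a 90% confidence interval within ±20 percentage points. The visible safety comparison has no such guard.

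**Working it through.** The plan gives no power or detectable difference for this test, so there is no figure to reproduce. The check asks how much sensitivity pooling costs under stated assumptions.

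**Inputs from the documents:** two-sided test, significance at p < 0.05 (SAP 5.1); Fisher's exact test on any TEAE (SAP 5.6).

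**Assumptions (not in the documents):**
- Arm size n = 100, 150 or 200 per active arm, with Test and Reference equal; 300 as a sensitivity case.
- Local TEAE rate on Reference L = 5%, 10%, 15% or 20%, doubled on Test.
- Unrelated TEAE rate b, equal in both arms and independent of local events; 20% as the base case, 10% and 30% as alternatives.

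**Step 1: dilution.** The chance of any TEAE is 1 − (1 − b)(1 − L). If local events go from L to 2L, the difference in any TEAE is (1 − b)L, against L for local events alone. For L = 10% and b = 20%:
- Reference: 1 − 0.80 × 0.90 = 28%.
- Test: 1 − 0.80 × 0.80 = 36%.
- The 10-point local difference becomes 8 points, on rates closer to 50%, where the variance is larger.

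**Step 2: exact power.** Sum Bin(x; n, p_R) × Bin(y; n, p_T) over all pairs (x, y) for which two-sided Fisher gives p < 0.05. Results for b = 20%, at n = 100 / 150 / 200:

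| Local TEAE, Reference → Test | Any TEAE, Reference → Test | Power, any TEAE | Power, local TEAE only |
|---|---|---|---|
| 5% → 10% | 24% → 28% | 7 / 10 / 12% | 19 / 30 / 41% |
| 10% → 20% | 28% → 36% | 18 / 28 / 36% | 44 / 63 / 77% |
| 15% → 30% | 32% → 44% | 36 / 53 / 66% | 67 / 85 / 94% |
| 20% → 40% | 36% → 52% | 59 / 78 / 88% | 84 / 96 / 99% |

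**Step 3: sensitivity to background and arm size.**
- L = 10%, n = 150: power on any TEAE is 40%, 28% and 21% for b = 10%, 20% and 30%.
- n = 300, L = 10%: 71%, 52% and 39% for the same backgrounds.
- n = 300, L = 5%: at most 28% for any b from 10% to 30%.
- In every cell computed, the pooled test had less power than the local-only test.

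**Step 4: the same loss as sample size.** For 80% power by the uncorrected formula, n = [1.96√(2p̄q̄) + 0.8416√(p_R q_R + p_T q_T)]² / d², with L = 10% and b = 20%:
- Any TEAE: [1.96√0.4352 + 0.8416√0.432]² / 0.08² = 3.408 / 0.0064 ≈ 533 per arm.
- Local only: [1.96√0.255 + 0.8416√0.25]² / 0.10² = 1.990 / 0.01 ≈ 199 per arm.

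**Step 5: what an interval would show.** Suppose those rates were observed with n = 150 (95% Wald interval, no correction):
- Any TEAE: SE = √[(0.28 × 0.72 + 0.36 × 0.64)/150] = 0.0537. The difference is 8.0 points, from −2.5 to 18.5.
- Local only: SE = √[(0.10 × 0.90 + 0.20 × 0.80)/150] = 0.0408. The difference is 10.0 points, from 2.0 to 18.0.

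The any-TEAE test is non-significant here, although its interval still allows an excess of more than 18 points. The p-value alone would not show that.

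**The case against.** **Arm sizes and rates are unknown.** A reader might infer that a doubling of local adverse events on Test would usually go undetected. The documents do not support that. The arm sizes are redacted, which is not a fault of the plan, and no event rate is given. The answer also turns on the local rate: from 20% the planned test has 59-88% power in the base case, and even from 10% it reaches 52% with 300 per arm. This objection stands against any unconditional statement. It does not touch the direction of the effect.

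**The plan does not rest on one p-value.** Application site events appear by preferred term, severity and relationship, and the graded reactions by visit. Protocol 2.2 compares safety on the kind, severity and frequency of events. A doubling of application site pain from 10% to 20% would be visible in those tables. This largely stands: such a difference would be missed by the test, not hidden from the reader. However, preferred terms split local events over several rows, no visible line counts subjects with any application site TEAE, and Protocol 8.1.5 names the pooled comparison as the basis for comparable safety.

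**The choice of Fisher's test.** A reader might also infer that the SAP departs from the protocol or hides harm by fixing Fisher's test. It does neither. Protocol 2.2 allows "Pearson's Chi-Square test or Fisher's Exact test, whichever is most appropriate, will be used to compare the proportion of subjects", and the SAP picks one of the two. Using Pearson on any TEAE would raise power only from 18/28/36% to 23/32/40% in the 10% case, and by about 1 to 6 points across the cells with a background. That is a preference, not a defect.

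**More tests alone would not help.** Two further significance tests would invite the same misreading, and the local-only test has just 44% power at n = 100 in the 10% case. This stands, and it is why the fix asks for estimates with intervals.

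**Redaction.** Text after the test sentence in Protocol 2.2 is redacted, so the statement that there is a single test covers the visible text only.

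**Conclusion.** The point holds in a limited form. The only visible inferential safety comparison of Test with Reference pools local with unrelated events, and Protocol 8.1.5 relies on it for comparable safety. Where unrelated events are equally common in both arms and independent of local ones, pooling shrinks a local difference by the factor (1 − b), and it lowered power in every case computed.

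The size of the loss is conditional. With 100 to 200 per arm and a 20% background, pooling costs about 12 to 28 percentage points of power from a 5% local rate (19 − 7 and 41 − 12 = 29 from the rounded figures), 26 to 41 points from 10% (44 − 18 and 77 − 36), and 11 to 25 points from 20% (99 − 88 and 84 − 59). Whether the planned test would in fact miss a doubling cannot be settled from the documents. It probably would at a local rate of about 5%; at 10% to 15% it depends on arm size and background; at 20% it mostly would not.

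What does follow is that a non-significant any-TEAE result should not by itself be read as comparable local safety. This is a low-cost improvement to the analysis and casts no doubt on the safety data to be collected.

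**What to change.** In SAP 5.6:

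1. Keep the any-TEAE comparison with Fisher's test as the overall line.
2. Add Test-Reference comparisons of subjects with any application site TEAE and subjects with any treatment-related TEAE. Define application site TEAE by a list of preferred terms fixed before unblinding.
3. Report all three as a difference in proportions with a confidence interval, and name the method and level. A 95% interval would match the two-sided 5% rule in SAP 5.1.
4. State that a non-significant any-TEAE test is not by itself evidence of comparable local safety, and that the new lines are read together with the by-visit table of graded reactions. Graded reactions that meet no trigger in Protocol 5.10 will still appear only in that table.

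No change of test from Fisher to Pearson is needed.

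The cost is SAP wording and two more rows in an existing table, from data already collected. The downside is two more unadjusted safety comparisons, which raise the chance of a spurious difference. That fits the no-adjustment policy in SAP 5.1, and reporting intervals limits the weight placed on any single p-value.

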6.1 Handling of Missing or Incomplete Dates for Adverse Events and Concomitant Medications

Adverse Events

Handling of partial dates is only considered for the start date. An adverse event with a partial start date is considered treatment emergent if:

- only the day is missing and the start month/year is the same or after the month/year of the first dose
- the day and month are missing and the start year is the same or greater than the year of the first dose date
- the start date is completely missing

Concomitant Medications

Handling of partial dates is only considered for the stop date. A medication with a partial stop date is considered concomitant if:

- only the day is missing and the stop month/year is the same or after the month/year of the first dose
- the day and month are missing and the stop year is the same or greater than the year of the first dose date
- the stop date is completely missing or the medication is ongoing

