5. PROCEDURES

5.1 Subject Screening and Enrollment

The study personnel will review the IRB approved informed consent form and assent form, if applicable, with each subject and give the subject an opportunity to have all questions answered before proceeding. The consent/assent form must be signed by each subject and witnessed before the subject is enrolled into the study. A copy of the signed consent/assent will be given to every subject and the original will be maintained with the subject's records. Subjects under the legal age of consent must sign an IRB approved written informed consent/assent in addition to a parent or legally authorized representative.

Subjects that require a wash-out [REDACTED] from their initial informed consent/assent signing must be re-consented before any further study procedures can begin.

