7.3 Eliciting and Reporting of Adverse Events

The investigator will periodically assess subjects for the occurrence of adverse events. In order to avoid bias in eliciting adverse events, the subject or parent/legally authorized representative should be asked a non-specific question (e.g., "How have you been feeling since your last visit?") to assess whether any AE has been experienced since the last visit. All adverse events (as defined in [Section 7.2](#)), either observed by the Investigator or one of his/her medical collaborators, or reported by the participant spontaneously, or in response to direct questioning, will be reported and documented in the source and the study reporting forms. When reporting an adverse event, the Investigator must assign a severity grade to each event and declare an opinion on the relatedness of the event to the study medication or procedure. Serious or unexpected adverse events must be reported to Perrigo and [REDACTED] **within 24 hours** of when the Investigator first learns of the occurrence of the event.

Adverse events will be documented in source and recorded in a timely manner on eCRFs. Adverse events (i.e., worsening of Actinic Keratosis*) that are identified at the last assessment visit (or the early termination visit), must be recorded on the AE eCRF with the status of the AE noted.

** Worsening of the subject's Actinic Keratosis may be expected from application of the study medication. Therefore, this will not be considered an AE unless one or more of the following occurs: 1) alternative treatment required; 2) subject is discontinued by the Principal Investigator for worsening of AK.*

Adverse event reporting begins from the signing of informed consent/assent. Adverse events should be followed until resolved or 30 days after the final study treatment. In any case, serious adverse events that are not resolved or considered to be chronic within 30 days of the final study treatment must be followed by the investigator until they become resolved or are considered to be chronic (stabilized for at least 30 days). All events that are ongoing at this time will be recorded as ongoing on the eCRF.

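### SAP 6.1 lets an adverse event with a partial or missing start date count as treatment-emergent even when its recorded stop date is before the first dose

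*SAP*

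**What the plan says.** SAP 5.6 (Adverse Events) gives the governing definition: a TEAE "is defined as any AE occurs on or after applying the first dose of study drug". The TEAE flag feeds the tables by body system and preferred term, severity and relationship, the table of events reported by 5% or more of subjects, and the Fisher's exact test of any TEAE between the two active arms.

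SAP 6.1 then covers incomplete dates. For AEs it begins "Handling of partial dates is only considered for the start date" and lists three conditions, any of which makes the event treatment-emergent:

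1. "only the day is missing and the start month/year is the same or after the month/year of the first dose"
2. "the day and month are missing and the start year is the same or greater than the year of the first dose date"
3. "the start date is completely missing"

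None of them mentions the stop date. The concomitant medication rule, in the same section, does compare the stop date with the first dose.

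Protocol 7.3 sets the collection period: "Adverse event reporting begins from the signing of informed consent/assent". Protocol section 9 requires consent before current medication is withdrawn for the study. Protocol 5.1 provides that subjects needing a washout (the qualifying length is redacted) "from their initial informed consent/assent signing must be re-consented before any further study procedures can begin". Protocol 2.2 has the end date of each AE recorded.

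**The concern.** Subjects who go through a washout have a period between consent and first dose in which AEs are recorded. An event that starts and ends in that period cannot have occurred on or after the first dose. If its start date is complete, the SAP 5.6 definition leaves it out. If its start date is incomplete, the SAP 6.1 conditions can bring it in, although a stop date already in the database settles the question.

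The proportion of subjects with any TEAE is the only between-arm safety test in SAP 5.6. Pre-dose events are unrelated to treatment, so counting them adds noise and pulls Test and Reference closer together. In a trial that sets out to show comparable safety, that is not clearly the conservative direction.

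**Working it through.** No figure in the documents depends on this rule, so there is nothing to reproduce. The check applies the conditions to example dates and then shows the direction of the effect under stated assumptions.

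**Step 1. Apply the rule as written.** Assume a first dose on 20 June 2015 (date chosen for illustration).

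| Recorded start | Recorded stop | SAP 6.1 as written | With stop-date condition |
|---|---|---|---|
| June 2015, day unknown | 12 June 2015 | TEAE (condition 1) | not TEAE |
| 2015, day and month unknown | 30 May 2015 | TEAE (condition 2) | not TEAE |
| no start date | 30 May 2015 | TEAE (condition 3) | not TEAE |
| May 2015, day unknown | 30 May 2015 | not TEAE | not TEAE |
| 2014, day and month unknown | 30 December 2014 | not TEAE | not TEAE |

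The first three rows ended before dosing and are still counted. The fourth row marks the limit of condition 1: when the month is known, it reaches a pre-dose event only if that event started in the month of the first dose. A washout event from an earlier month is reached only through condition 2 (same year) or condition 3.

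**Step 2. How far each condition reaches.** Assume the first dose falls uniformly over one calendar year and a pre-dose event starts uniformly over the L days before it. The washout length is redacted, so L is varied. The table shows the share of such starts that the rule classes as treatment-emergent. The problem further requires that the event also ended before dosing.

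| L (days) | Day unknown (condition 1) | Day and month unknown (condition 2) |
|---|---|---|
| 7 | 86.8% | 98.9% |
| 14 | 75.3% | 97.9% |
| 30 | 49.1% | 95.8% |
| 60 | 24.5% | 91.6% |
| 90 | 16.4% | 87.5% |

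Condition 3 captures 100% whatever the window.

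**Step 3. Effect on the any-TEAE rate.** Let p be an arm's true any-TEAE rate and q the share of its subjects with a misclassified pre-dose event, independent of true TEAEs and equal between arms. A subject with a genuine TEAE is already counted, so

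observed rate = p + q(1 − p), and observed difference = (1 − q)(p1 − p2).

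For q = 2%: 0.30 + 0.02 × 0.70 = 0.314 and 0.15 + 0.02 × 0.85 = 0.167, a difference of 0.147.

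**Step 4. Effect on the test.** The true rates of 30% and 15% and the 150 subjects per arm are assumptions; the sample size section is redacted. Power is for a two-sided Fisher's exact test at 0.05, by enumeration of both binomial distributions.

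| q per arm | Observed rates | Difference (points) | Power |
|---|---|---|---|
| 0% | 30.0% vs 15.0% | 15.00 | 0.855 |
| 1% | 30.7% vs 15.85% | 14.85 | 0.838 |
| 2% | 31.4% vs 16.7% | 14.70 | 0.822 |
| 5% | 33.5% vs 19.25% | 14.25 | 0.770 |

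Under these assumptions the direction follows from the factor (1 − q). The size depends entirely on q, which the documents do not give.

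**The case against.** The opening sentence of the AE rule can be read as saying only that partial stop dates are not imputed. A complete stop date is not a partial date, and SAP 5.6 still governs, so a careful programmer might exclude the event. That reading is possible, and it means the SAP does not expressly order complete stop dates to be ignored. But the three conditions carry no exception, and a programmer who codes them as listed will flag the event.

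Treating an ambiguous date as treatment-emergent is a sound conservative default. That stands and should be kept. The problem is limited to dates that the stop date makes unambiguous.

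The required combination is rare. SAP section 3 lists no visit before Day 1, and Protocol 5.11 has the first dose applied at that visit, so subjects without a washout have a very short pre-dose period. Screen failures are not entered in the database (Protocol 5.14), and missing data are queried before lock (Protocol 10.1). All of this stands and limits the size.

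A reader might infer that the day-unknown condition sweeps in washout events generally. It does not, as Step 1 shows. A reader might also picture an event several months before dosing being counted. The rule would allow it, but with the washout length redacted the documents do not show that so long a gap can occur.

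**Conclusion.** The point holds as an inconsistency between SAP 6.1, read literally, and the TEAE definition in SAP 5.6. An AE known to have ended before the first dose is counted in three situations: day unknown with a start in the month of first dose; day and month unknown with a start in the year of first dose; or no start date.

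The consequence is minor. The frequency is unknown and probably very small. Events before dosing are balanced between randomised arms in expectation, so the documents do not support an inference that one arm is favoured; the effect is a slight shift toward no difference. Nor does a share q of affected subjects raise the any-TEAE rate by the full q: at an assumed base rate of 30%, q = 2% adds 1.4 points. The primary efficacy analysis is untouched. The figures rest on the assumed rates, arm size, equal q in both arms and independence stated above.

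**What to change.** Add one sentence to the AE part of SAP 6.1, before unblinding: *An AE with a partial or missing start date is not treatment-emergent if its stop date (complete, or partial but unambiguously earlier by month/year) is before the date of first dose.* Keep the three existing conditions as the default for every other ambiguous date, including events with no informative stop date.

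The cost is one extra condition in the TEAE derivation, including a simple month/year comparison for partial stop dates that the AE rule does not now have. No new data are needed.
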